2.4.9 Analyses of quality of life/health economics variables

See [Section 2.4.4.4.6](#) and [Section 2.4.4.4.7](#).

2.5 DATA HANDLING CONVENTIONS

2.5.1 General conventions

The following formulas will be used for computation of parameters.

Study day

Study day = assessment date - first IMP injection date + 1 (if assessment date \geq first IMP injection date), otherwise study day = assessment date - first IMP injection date, the day of first IMP injection being Day 1. For randomized but not treated patients, Day 1 is the day of randomization.

Demographic formulas

Age (years) = (date of informed consent - date of birth)/365.25

Renal function formulas

Creatinine clearance value will be derived using the equation of Cockcroft and Gault:

For male:

$$CL_{CR} \text{ (mL/min)} = \frac{(140 - age(\text{years})) * weight(\text{kg})}{0.814 * serumcreatinine(\mu\text{mol/L})}$$

For Female: result above multiplied by 0.85.

Date of last dose of investigational medicinal product

The date of the last dose of IMP is equal to the last date of administration reported on the IMP administration case report form page, or missing if the last administration date is unknown.

Lipids variables, laboratory safety variables, hs-CRP

For data below the lower limit of quantification (LLOQ)/limit of linearity, half of the lower limit value (ie, LLOQ/2) will be used for quantitative analyses. For data above the upper limit of quantification (ULOQ) / limit of linearity, the upper limit value (ie, ULOQ) will be used for quantitative analyses.

For ANCA parameter: values “<1:20” are considered as negative; other results are considered as positive.

2.5.2 Data handling conventions for efficacy variables

Handling of CRISS missing data

Two different methods will be used to impute CRISS missing data, depending on the nature of the missing item.

If the missing item at a given time-point relates to organ involvement (Step 1 of CRISS derivation):

- If there was already an organ involvement at a previous post-baseline time-point (CRISS already evaluated as 0 at a previous time point), CRISS will be imputed the value of 0.
- Otherwise, if at the current time-point, one organ has worsened (CRISS evaluated as 0 due to new or worsening of another organ for which the evaluation is non missing), CRISS will be imputed the value of 0.
- Otherwise, if no other organ has worsened, as such an event should have been classified as a serious adverse event, it is assumed that no organ had worsened otherwise the event would have been recorded, so CRISS will be derived using Step 2. Each missing component (FVC, DLco, mRSS, PT-glob, MD-glob and HAQ-DI) at Week 24 will be imputed using the method explained below.

Handling of FVC, DLco and CRISS missing data

In order to impute the FVC, DLco and CRISS missing data at Week 24, the following steps will be performed:

- Patients in active arm and taking treatment at Week 24 (treatment discontinuation is defined for this analysis as last injection + 7 days): Missing values at Week 24 will be imputed using a model estimated from the subset of patients in the active arm who completed the 24-week treatment period and with a Week 24 value. The imputation model will be based on a MMRM with fixed categorical effect of stratification (as per IRT, with/without ILD) and repeated categorical effect for time point (baseline, Week 4 (except for % predicted DLco and % predicted FVC), Week 8 (except for % predicted DLco and % predicted FVC), Week 12 and Week 24). Parameters will be estimated with the Newton-Raphson algorithm, an unstructured covariance matrix will model the within-patient errors, and the denominator degrees of freedom will be estimated using Kenward-Roger's approximation. Missing values at Week 24 will be imputed using the Empirical Best Linear Unbiased Prediction (EBLUP).
- Other patients (patients in active arm and not taking treatment at Week 24; or patients in placebo arm): Missing values at Week 24 will be imputed similarly but using a model estimated from the subset of patients in the placebo arm who completed the 24-week treatment period and with a Week 24 value.
- When running the imputation model:
 - If the mRSS value is inferior to 0, then it will be set to 0. If the mRSS value is superior to 51, it will be set to 51,
 - If the % predicted FVC value is inferior to 0, it will be set to 0,
 - If the % predicted DLco value is inferior to 0, it will be set to 0,
 - If the PT-glob value is inferior to 0 or superior to 10 it will be set to 0 and respectively to 10,
 - If the MD-glob value is inferior to 0 or superior to 10, it will be set to 0 and respectively to 10,
 - If the HAQ-DI value is inferior to 0 or superior to 3, it will be set to 0 and respectively to 3.

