9.1.4.5 Cardiac Manifestations

Systemic sclerosis associated cardiac manifestations will be assessed by physical examination and ECG which is an established method of monitoring for cardiac conduction and potential coronary and myocardial diseases. Electrocardiogram will be captured at all scheduled visits except Visit 3. Cardiovascular events will be reported as AEs.

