10.4.1.2 Serious adverse event

A SAE is any untoward medical occurrence that at any dose:

- Results in death, or
 - Is life-threatening, or
- Note: The term “life-threatening” in the definition of “serious” refers to an event in which the patient was at risk of death at the time of the event; it does not refer to an event which hypothetically might have caused death if it were more severe.
- Requires inpatient hospitalization or prolongation of existing hospitalization, or
 - Results in persistent or significant disability/incapacity, or
 - Is a congenital anomaly/birth defect
 - Is a medically important event.

Medical and scientific judgment should be exercised in deciding whether expedited reporting is appropriate in other situations, such as important medical events that may not be immediately life-threatening or result in death or hospitalization but may jeopardize the patient or may require medical or surgical intervention (ie, specific measures or corrective treatment) to prevent one of the other outcomes listed in the definition above.

Note: The following list of medically important events is intended to serve as a guideline for determining which condition has to be considered a medically important event. The list is not intended to be exhaustive:

- Intensive treatment in an ER or at home for:
 - Severe hypersensitivity reactions (anaphylaxis, allergic bronchospasm [see [Appendix I](#) for the clinical criteria for diagnosing anaphylaxis])
 - Blood dyscrasias (ie, agranulocytosis, aplastic anemia, bone marrow aplasia, myelodysplasia, pancytopenia),
 - Convulsions (seizures, epilepsy, epileptic fit, absence, etc).
- ALT >3 x ULN + TBILI >2 x ULN or asymptomatic ALT increase >10 x ULN. See [Appendix K](#).
- Suicide attempt or any event suggestive of suicidality.
- Syncope, loss of consciousness (except if documented as a consequence of blood sampling)
- Bullous cutaneous eruptions.
- Cancers diagnosed during the study or recurs during the study
- Chronic neurodegenerative diseases (newly diagnosed) or aggravated during the study (only if judged unusual/significant by the Investigators in studies assessing specifically the effect of a study drug on these diseases).

- Suspected transmission of an infectious agent via a medicinal product (eg, product contamination).

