The digital ulcer count corresponds to the sum of active or new plus indeterminate/healing digital ulcers secondary to SSc (see [Appendix I](#)).

- CRISS.

The Composite Response Index for Diffuse Cutaneous Systemic Sclerosis (CRISS) tool summarizes the changes in the clinical and patient-reported outcomes using a single composite score that reflects the probability that the patient with dcSSc has improved.

CRISS is obtained in a 2-step process as described below.

Step 1: Patients who develop new or worsening of cardiopulmonary and/or renal involvement due to SSc are considered as not improved (irrespective of improvement in other core items) and assigned a probability of improving equal to 0.0. Specifically if a subject develops any of the following:

- New scleroderma renal crisis.
- Decline in FVC% predicted $\geq 15\%$ (relative), confirmed by another FVC% within a month, high resolution computer tomography (HRCT) to confirm ILD (if previous HRCT of chest did not show ILD) and FVC% predicted below 80% predicted*.
- New onset of left ventricular failure (defined as left ventricular ejection fraction $\leq 45\%$) requiring treatment*.
- New onset of Pulmonary Arterial Hypertension (PAH) on right heart catheterization requiring treatment*. PAH is defined as mean pulmonary artery pressure ≥ 25 mm Hg at rest and an end-expiratory pulmonary artery wedge pressure ≤ 15 mm Hg and a pulmonary vascular resistance > 3 Wood units.

*Attributable to SSc

Step 2: For the remaining patients, Step 2 involves computing the predicted probability of improving for each subject using the following equation (equation to derive predicted probabilities from a logistic regression model):

$$\frac{\exp(-5.54-0.81*\Delta\text{MRSS}+0.21*\Delta\text{FVC\%}-0.40*\Delta\text{Pt-glob}-0.44*\Delta\text{MD-glob}-3.41*\Delta\text{HAQ-DI})}{1+\exp(-5.54-0.81*\Delta\text{MRSS}+0.21*\Delta\text{FVC\%}-0.40*\Delta\text{Pt-glob}-0.44*\Delta\text{MD-glob}-3.41*\Delta\text{HAQ-DI})}$$

ΔmRSS indicates the change in mRSS from baseline, $\Delta\text{FVC\%}$ denotes the change in FVC% predicted from baseline, $\Delta\text{Pt-glob}$ indicates the change in patient global assessment (as per Likert scale), $\Delta\text{MD-glob}$ denotes the change in physician global assessment (as per Likert scale) (see [Appendix G](#)), and $\Delta\text{HAQ-DI}$ is the change in HAQ-DI. All changes are absolute change ($\text{Time}_2 - \text{Time}_{\text{baseline}}$).

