2.4.4.4.10 CRISS

The distribution of the predicted probability of improving obtained using the CRISS at Week 24 and Week 35 will be compared between SAR156597 and the placebo group using a Van Elteren's test stratified on randomization strata.

In case of more than 20% of missing data on the CRISS value at Week 24, missing data will be imputed following methods described in [Section 2.5.2](#). Otherwise, the data will not be imputed.

In addition, rate of patients for whom the predicted probability of improving obtained using the CRISS at Week 24 and Week 35 is $\geq 60\%$ will be provided.

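### The CRISS rule reads a missing organ item as no worsening because a worsening would have been an SAE; that premise fails for a missed FVC

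*SAP*

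**What the plan says.** SAP 2.1.4 builds CRISS in two steps. Step 1 scores a patient 0.0 for any of four organ events attributed to SSc: renal crisis, a decline in FVC, treated left ventricular failure, or treated PAH. The FVC event is a relative fall of at least 15% in % predicted FVC to below 80% predicted, "confirmed by another FVC% within a month, high resolution computer tomography (HRCT) to confirm ILD" if ILD had not been shown before. Everyone else gets a probability from the Step 2 equation.

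SAP 2.5.2 handles a missing Step 1 item in three branches:

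- "If there was already an organ involvement at a previous post-baseline time-point", CRISS is set to 0.
- "Otherwise, if at the current time-point, one organ has worsened", CRISS is set to 0.
- In all other cases, "as such an event should have been classified as a serious adverse event, it is assumed that no organ had worsened". Step 2 is used, with missing components imputed at Week 24.

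SAP 2.4.4.4.10 decides when this applies: "In case of more than 20% of missing data on the CRISS value at Week 24, missing data will be imputed". At or below that level the values stay missing. The same section compares the arms with a Van Elteren test and reports the rate of patients at or above 60%.

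On seriousness, Protocol 10.4.1.2 gives general criteria, such as "Requires inpatient hospitalization or prolongation of existing hospitalization", and an open list of medically important events. Neither names a Step 1 event. Protocol 9.1.4.5 says: "Cardiovascular events will be reported as AEs".

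**The concern.** The third branch infers that nothing happened from the absence of an SAE. That works only if each Step 1 event would have to appear as an SAE. The protocol does not require this, and for the FVC item it cannot happen without a test: the event consists of spirometry results, so a missed spirometry produces no event to report.

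At stake is a patient whose lung function has fallen far enough to meet Step 1 if tested and confirmed, but who is scored by Step 2 with a milder, predicted FVC. If skin or other items have improved, the score can pass 60%.

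**Working it through.** **Is each Step 1 event bound to appear as an SAE?**

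- Renal crisis: acute renal failure is an AESI (Protocol 10.4.1.3), notified within 24 hours (10.4.5). An AESI may be non-serious.
- Left ventricular failure and PAH requiring treatment: reported as AEs under 9.1.4.5. They are serious if they meet a general criterion or are judged medically important.
- FVC decline: Protocol 10.4.3 says when laboratory, vital-sign and ECG abnormalities become AEs and does not mention lung function tests. The flow chart (Protocol 1.2) schedules post-baseline lung function tests at Weeks 12, 24 and 35 only, with no confirmatory FVC and no HRCT. Footnote n says Step 1 rests on available data.

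For the first three, some safety record is likely. For a missed FVC, none is implied.

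**What happens next?** Under SAP 2.5.2 the missing Week 24 FVC is predicted (EBLUP) from a model fitted to completers with a Week 24 value: active-arm completers for active patients still on treatment, placebo completers for everyone else. Predictions are only clipped to the range of the scale. They are not compared with the Step 1 FVC limits.

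**What score results?** The plan states no figure for this rule, so there is none to reproduce; its power calculation concerns mRSS. The Step 2 equation (SAP 2.1.4) is

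logit = -5.54 - 0.81 x change in mRSS + 0.21 x change in FVC% - 0.40 x change in patient global - 0.44 x change in physician global - 3.41 x change in HAQ-DI.

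Assumed patient: mRSS change -8; globals and HAQ-DI unchanged; FVC falls from 78% to 64% predicted. The relative fall is 14/78 = 17.9%, and 64 is below 80, so the size limits of Step 1 are met. A baseline of 78% does not trigger exclusion E 12. Without FVC the logit is -5.54 + 6.48 = 0.94.

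| FVC change used | Logit | CRISS | At or above 0.60 |
|---|---|---|---|
| 0 (imputed) | 0.94 | 0.72 | yes |
| -2 (imputed) | 0.94 - 0.42 = 0.52 | 0.63 | yes |
| -3 (imputed) | 0.94 - 0.63 = 0.31 | 0.58 | no |
| -14 (true value in Step 2) | 0.94 - 2.94 = -2.00 | 0.12 | no |
| Step 1 event confirmed | not used | 0.00 | no |

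The 0.60 cut is a logit of ln(0.6/0.4) = 0.405, so this patient passes if the imputed FVC change is above (0.405 - 0.94)/0.21, or about -2.5 points.

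With modest gains elsewhere (each global -1, HAQ-DI -0.25), imputed FVC changes of 0 and -3 give 0.73 and 0.59 at mRSS -6, and 0.93 and 0.88 at mRSS -8. With every change at zero the score is 0.004.

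**How many patients?** 20% of 94 is 18.8, so at least 19 Week 24 CRISS values must be missing before any is imputed. One misclassified patient moves the rate in an arm of 47 by up to 1/47 = 2.1 points.

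**The case against.** The best defence is that the rule is narrower and better protected than its last branch suggests. The two preceding branches set CRISS to 0 after an earlier or concurrent organ event. Lung function and Step 1 are assessed at Week 12, so an event established by then carries forward, and an unconfirmed early decline still informs the imputed value through the repeated-measures model. All AEs are recorded whatever their seriousness (Protocol 10.4.3), and renal crisis or treated cardiac disease or PAH could well be serious. All of this stands, and it confines the defect largely to an FVC decline after Week 12.

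The 20% condition may also never be met. The plan assumes 10% treatment discontinuation and asks those patients to attend Week 24 (Protocol 11.1, 10.3.4). That stands too.

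A reader might infer more than the documents support:

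- That at least 19 patients would fall under this rule. The 20% counts CRISS values missing for any reason, including a missing mRSS, global or HAQ-DI. The number missing a Step 1 item could be far smaller, or zero.
- That missing echocardiograms or catheterizations feed the rule. Echocardiography is scheduled only at screening and right heart catheterization not at all, so no planned post-baseline result can be missed.
- That the rule favours the arm with more organ deterioration. The documents give no rates of missing FVC or organ events by arm.

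What does not stand is the stated reason. Absence of an SAE says nothing about an FVC that was not measured.

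**Conclusion.** The concern holds in a limited form. The SAE premise is unsupported as a general statement and fails outright for a missed Week 24 FVC. The rule can then give a score above 0.60 where a tested and confirmed decline would give 0.

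The examples rest on assumed item changes, an assumed imputed FVC change between 0 and -3 points, and a decline that would have been confirmed and attributed to SSc. Only patients who improve on skin or other items can cross 0.60. The effect is up to 2.1 points on one arm's rate per misclassified patient. The number of such patients, and the size and direction of any between-arm bias, cannot be computed.

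CRISS is exploratory and its p-values are descriptive (SAP 2.4.4.3), so no primary or secondary analysis is affected. A related gap is that the overall responder definition in SAP 2.4.4.4.1 requires no CRISS event but does not say how a missing organ item counts.

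**What to change.** In SAP 2.5.2, replace the SAE premise as follows:

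1. Screen all recorded AEs, AESIs and SAEs for the four Step 1 events, blind to treatment. Set CRISS to 0 where the Step 1 definition is met. A term search alone will not establish LVEF, catheter findings or attribution to SSc, so flagged cases need review.
2. State that a missing FVC is not evidence of no decline. For cases still unresolved, keep the current handling in the main analysis, labelled as an assumption, and report their number by arm.
3. Add a sensitivity analysis that scores unresolved organ items, FVC in particular, as CRISS = 0.
4. State how a missing organ item counts in the overall responder definition.

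Do not apply the FVC limits to imputed values with confirmation waived in the main CRISS analysis. An imputed fall would then score 0 where an observed but unconfirmed one does not, contrary to SAP 2.1.4.

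The cost is SAP wording, some programming and a blinded case review, with no new visits or tests. Some CRISS values will become less favourable.

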2.4.4.1 Analysis of primary efficacy endpoint(s)

2.4.4.1.1 Primary efficacy analysis

The primary estimand will be the difference in mean change from baseline to 24 weeks in mRSS in all randomized patients, regardless of whether or not patients completed the treatment period. This estimand corresponds to a “treatment policy strategy”.

A spaghetti plot presentation of individual data by treatment group will be presented.

The change in mRSS from baseline to Week 24 will be analyzed in the ITT population using a MMRM approach. All post-baseline data available from Week 4 to Week 24 analysis windows will be included in the analysis, regardless of adherence to treatment. The lower the mRSS is, the better it is for the patient.

Missing data will be accounted for by the MMRM. The model includes the fixed categorical effects of treatment group (placebo, SAR156597), randomization strata (as per IRT, SSc-ILD: Yes/No), time point (Week 4, Week 8, Week 12, Week 24 as defined in [Section 2.5.4](#)), randomization strata-by-time point interaction and treatment-by-time point interaction, as well as the continuous fixed covariates of baseline mRSS value and baseline value-by-time point interaction.

This model will be run using SAS Mixed procedure. The repeated-measures analysis will be based on the restricted maximum likelihood method (Newton-Raphson algorithm) assuming an unstructured correlation matrix to model the within-patient errors. Denominator degrees of freedom will be estimated using Kenward-Roger approximation. This model will provide baseline adjusted LSmeans estimates at Week 24 for both treatment groups with their corresponding standard errors (SEs) and 95% confidence intervals (CIs). To compare SAR156597 to the placebo group, an appropriate contrast statement will be used to test the difference of these estimates at the 5% one-sided alpha level. The 95% and 90% confidence intervals of the difference will be provided. Let μ_0 and μ_1 be the population means of the change from baseline in mRSS at Week 24 under placebo and SAR156597, respectively. The null hypothesis that will be tested is “ $H_0: \mu_0 = \mu_1$ ” versus “ $H_1: \mu_0 > \mu_1$ ”.

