2.4.4.4.8 FVC

Due to the non-normality of the distribution of % predicted FVC, the change from baseline at Week 24, respectively Week 35, will be analyzed using a rank-based analysis of covariance (rank analysis of covariance [ANCOVA]) model adjusted for baseline and stratified on randomization stratum (as per IRT). This model will use the ranks of absolute change from baseline to Week 24 (respectively Week 35) in % predicted FVC as the outcome and the ranks of baseline % predicted FVC as a covariate stratified on the stratification factor (with/without ILD). In case of ties, the mean of the corresponding ranks will be assigned.

The ranking will be done within each stratum of the stratification factor (with/without ILD) in ITT population (both treatment groups combined).

- Missing data due to death will be ranked based on a time-to-death, with shortest time until death as the worst (lowest) rank (from 1 to $n_{\text{stratum, death}}$).
- Absolute change from baseline at Week 24 (respectively Week 35) in % predicted FVC values will be calculated from Week 24 (respectively Week 35) % predicted FVC values and then ranked (from $n_{\text{stratum, death}} + 1$ to n_{stratum}).
- Standardization of ranks using SAS PROC RANK.

Furthermore, the adjustment on baseline % predicted FVC covariate will be done. The residuals from the linear regression of response ranks on baseline ranks will be calculated within each stratum of the stratification factor (with/without ILD).

Finally, treatment effect will be tested using the residuals as scores. The active treatment group will be compared to placebo using a Mantel-Haenszel mean score chi-square test at a one-sided Type-I error level of 5%. This test will be stratified on the stratification factor.

In case of more than 20% of missing data on the % predicted FVC value at Week 24, missing data will be imputed following methods described in [Section 2.5.2](#). Otherwise, the data will not be imputed.

Furthermore, the change in observed FVC from baseline to Week 35 will be analyzed using the MMRM model described in [Section 2.4.4.4](#).

The number of patients with an absolute decreased % predicted FVC from baseline at W24 superior or equal to 5% and respectively 10% will be presented by treatment group.

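### As written, the SAP 2.5.2 imputation model for missing Week 24 % predicted FVC, % predicted DLco and CRISS components has no mean effect of time, so imputed values are pulled towards no change from baseline

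*SAP*

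**What the plan says.** SAP 2.5.2 sets out how missing Week 24 values of % predicted FVC, % predicted DLco and the CRISS components are filled in. The model is an "MMRM with fixed categorical effect of stratification (as per IRT, with/without ILD) and repeated categorical effect for time point". Its time levels are given as "repeated categorical effect for time point (baseline, Week 4 (except for % predicted DLco and % predicted FVC", and so on to Week 24, so baseline is a response and not a covariate. For the covariance, "an unstructured covariance matrix will model the within-patient errors". The filled-in value is a single prediction: "Missing values at Week 24 will be imputed using the Empirical Best Linear Unbiased Prediction (EBLUP").

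Two models are fitted, each in patients who completed the 24-week treatment period and have a Week 24 value. Active patients still on treatment at Week 24 are predicted from active completers. Everyone else is predicted from placebo completers: "Other patients (patients in active arm and not taking treatment at Week 24; or patients in placebo arm").

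The step is conditional. For FVC (SAP 2.4.4.4.8): "In case of more than 20% of missing data on the % predicted FVC value at Week 24, missing data will be imputed". For CRISS (SAP 2.4.4.4.10): "In case of more than 20% of missing data on the CRISS value at Week 24, missing data will be imputed". SAP 2.4.4.4.9 applies the FVC method to % predicted DLco.

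By contrast, the primary model in SAP 2.4.4.1.1 lists among its fixed effects "time point (Week 4, Week 8, Week 12, Week 24 as defined in" the windows section. SAP 2.4.4.2 and 2.4.4.4 also name time point as a fixed effect. Nothing in the SAP adds it to the imputation model.

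**The concern.** In a repeated-measures model, the repeated effect indexes the covariance matrix. It adds no term to the mean. With stratum as the only fixed effect, the model says that average FVC or mRSS is the same at baseline and at Week 24. The average change seen in the completers is then largely not passed on to the patients being imputed.

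Two things are at stake. First, the imputed values are biased whenever the measure drifts over time. Drawing multiple imputations from the same model would not cure that. Second, if one arm has more missing data, the lost drift appears as a treatment difference. On a declining FVC or DLco, the arm with more missing data looks better. On an improving mRSS within CRISS, it looks worse.

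**Working it through.** **Figures in the plan.** The SAP states no figure for this step. The only computed design figure is the power, and it reproduces: Φ(3.6 / (7·√(2/47)) - 1.645) = Φ(2.493 - 1.645) = Φ(0.848) = 0.80. The point does not depend on it.

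**The model written out.** Y(i,t) = μ(stratum) + e(i,t), with e multivariate normal and an unstructured covariance Σ. Let ȳ be the completers' visit means and S their covariance matrix. Maximum likelihood gives

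- μ̂ = (1'S⁻¹ȳ) / (1'S⁻¹1)
- Σ̂ = S + (ȳ - μ̂1)(ȳ - μ̂1)'

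The misfit in the mean is absorbed into the covariance.

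**FVC, closed form.** Assumptions (none are in the documents): SD 15 at each visit; mean change 0, -1.5 and -3 at baseline, Week 12 and Week 24; correlation ρ between baseline and Week 24. By symmetry μ̂ = -1.5, so ȳ - μ̂1 = (1.5, 0, -1.5).

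*Baseline only known, patient at the baseline mean.* Imputed change = -1.5 × [1 - (225ρ - 2.25)/(225 + 2.25)].
- ρ = 0.9: -1.5 × (1 - 200.25/227.25) = -0.18
- ρ = 0.5: -1.5 × (1 - 110.25/227.25) = -0.77

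*Week 12 also known, ρ = 0.9, patient at the baseline and Week 12 means.*
- Equal correlations: the weight on the baseline residual is (225×200.25 - 202.5²)/(227.25×225 - 202.5²) = 4050/10125 = 0.40. Imputed change = -1.5 + 0.40×1.5 = -0.90.
- Serial correlation (adjacent visits √0.9): the weight is (225×200.25 - 45562.5)/(227.25×225 - 45562.5) = -506.25/5568.75 = -0.09. Imputed change = -1.5 - 0.09×1.5 = -1.64.

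**Large simulated samples** (ρ from 0.5 to 0.9, both correlation patterns) agree:

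| Measure, true change | Baseline only | Through Week 12 | With fixed time |
|---|---|---|---|
| FVC, -3 (SD 15) | -0.2 to -0.8 | -0.9 to -1.7 | about -3.0 |
| mRSS, -4 (SD 7) | -0.3 to -1.2 | -1.4 to -2.9 | about -4.0 |

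If change is independent of baseline level, the baseline-only values go to about 0. The baseline-only ranges are therefore best read as about 0 to -0.8 for FVC and about 0 to -1.2 for mRSS.

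**CRISS.** The SAP's coefficient is 0.81 per mRSS point. At a true -4, the shortfall lowers the CRISS logit by 0.81×(4 - 1.2) = 2.3 up to 0.81×4 = 3.2 with baseline only. With visits through Week 12 it lowers it by 0.81×(4 - 2.9) = 0.9 up to 0.81×(4 - 1.4) = 2.1.

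**Between-arm effect, no true treatment effect.** Assumptions: 47 per arm, shared FVC change -3, half of dropouts with Week 12 observed, all active dropouts off treatment and so imputed from placebo completers as SAP 2.5.2 directs, and the stratified rank test at one-sided 5%. The first two rows use baseline SD 14 and SD of change 6. The last two use SD 15 and correlation 0.9.

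| Missing, active v placebo | Spurious difference | Favours arm with more missing, as written | Same, fixed time |
|---|---|---|---|
| 30% v 13% | +0.30 | 8.1% | 3.6% |
| 40% v 10% | not tabulated | 12.6% | 1.7% |
| 35% v 15% | +0.41 | 10.3% | 3.1% |
| 15% v 35% | -0.43 | 9.6% | 6.5% |

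A further run at 30% v 13% gave 8.5% as written and 3.1% with fixed time. With equal missingness (21% or 25% per arm) the rate is about 5% each way and the difference about 0. Monte Carlo error in the last two rows is about 0.5 to 1 percentage point.

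**Reaching the trigger.** 30% and 13% of 47 is 14.1 + 6.1 = 20.2 of 94, or 21.5%. That is just over the 20% threshold if it is counted over both arms. The planning assumption of 10% treatment discontinuation is 9.4 of 94.

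**The case against.** **The wording may be shorthand.** Every MMRM that the SAP spells out has a fixed time or visit term, and the authors may have meant the repeated time effect to carry a mean. That is possible, so the documents do not show that the omission was intended. But the sentence separates fixed from repeated effects, and a programmer following it would put only stratum in the mean model. The text needs correcting on either reading.

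**The consequence is remote and limited.** The step runs only above 20% missing at Week 24. Protocol 10.3.4 asks patients who stop treatment to keep attending, naming FVC and DLco, and the Week 24 window runs from day 127 to day 207. A spurious difference needs both a mean trend and unequal missingness, and the documents give no basis for 30% v 13%. The endpoints are exploratory, and SAP 2.4.4.3 makes their p-values descriptive. All of this stands and sets the weight of the point.

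**Stronger readings a reader might infer.**
- That imputed patients in general lose most of any real change. This holds with baseline only. With Week 12 known, FVC keeps 0.9/3 = 30% to 1.7/3 = 57%, and mRSS keeps 1.4/4 = 35% to 2.9/4 = 73%. Active patients still on treatment at Week 24 would normally have the earlier visits.
- That the trial's type I error is at risk. It is not: the primary mRSS model and the secondary observed FVC and DLco models have time point as a fixed effect and do not use this step.
- That adding time restores the nominal error rate. It does not: the rates with fixed time range from about 2% to 7%, because single imputation still misstates the variance.

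**Conclusion.** The point holds on the text as written. Under SAP 2.5.2, baseline and Week 24 share one mean, and predicted Week 24 values are pulled towards no change. Under the stated assumptions:

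- A true FVC change of -3 becomes about 0 to -0.8 with baseline only, and -0.9 to -1.7 with Week 12 known.
- A true mRSS change of -4 becomes about 0 to -1.2 with baseline only, and -1.4 to -2.9 with visits through Week 12.
- With a shared FVC decline of -3 and no treatment effect, one-sided false results favouring the arm with more missing data are about 8% at 30% v 13% missing and about 13% at 40% v 10%, against about 2-4% with fixed time.

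The bias in the imputed values needs only a mean trend. The spurious treatment difference also needs unequal missingness. The rule should be corrected because it operates only when missing data are heavy, which is when imputed values carry most weight. It does not threaten the trial's main conclusion.

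**What to change.** In SAP 2.5.2, replace the model description with: *MMRM with fixed categorical effects of stratification (as per IRT) and time point, with time point also as the repeated effect (unstructured covariance)*. Fit it in the same active and placebo completer subsets as now planned. A stratification-by-time point term is optional if the strata are large enough; it is not needed to remove the bias in the mean.

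The cost is one sentence, one added model term in the code and a few extra mean parameters per fit. In the simulations, the mean imputed change then matches the true mean change to within 0.1 point and the spurious between-arm difference falls to about 0. The understated variance from imputing a single predicted value is a separate matter that this change does not address.
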